7.2 Enrollment/screening Period

The following assessments and procedures should be performed within 28 days prior to first dose of study treatment. For details of the schedule and nature of the assessments, see below.

- Signed informed consent for the study; include main inform consent
- Results of EBV IHC or PDL1 (EBV positive or PDL1 CPS≥5)

EBV test: (all centralized at CAP-certified pathology lab/SMC): he entire procedure was performed on a fully automatic system (BOND-MAX) for in situ hybridization with an EBV-encoded RNA probe from Leica (Newcastle, UK) following manufacturer's instructions (ref: Gastroenterology [Type here] [Type here] [Type here])

Pembrolizumab + Ramucirumab (Ver 2.5, Oct 2024)
2010 vol 139, pages 84-92).

PDL1 test: IHC staining will be carried out on Dako Autostainer Link 48 system (Agilent Technologies, Santa Clara, CA) using Dako PD-L1 IHC 22C3 pharmDx kit (Agilent Technologies) with EnVision FLEX visualization system and counterstained with hematoxylin according to the manufacturer's instructions. PD-L1 protein expression will be determined by using Combined Positive Score (CPS), which was the number of PD-L1 staining cells (tumor cells, lymphocytes, macrophages) divided by the total number of viable tumor cells, multiplied by 100. (ref: https://www.agilent.com/cs/library/usermanuals/public/29158_pd-l1-ihc-22C3-pharmdx-nslcl-interpretation-manual.pdf)

- Date of birth, race and ethnicity
- Medical and surgical history
- Current and concomitant medications including previous cancer therapies (if applicable)
- Physical examination
- ECOG performance status
- Vital signs (blood pressure, pulse and body temperature), body weight and height.
- Hematology, clinical chemistry and urinalysis, TFT
- Menopausal status; serum or urine pregnancy test for women of childbearing potential (within 7 days prior to study treatment start
- ECG
- Echocardiogram/MUGA Should be completed if patients had received prior anthracycline therapy
- Tumor assessment (scans of the abdomen/pelvis/other sites as clinically indicated for assessment of disease [CT/MRI]), performed within 14 days prior to enrollment, ideally should be performed as close as possible to the start of the treatment. Scans that were performed as part of standard of care prior to signature of the informed consent form can be analysed for the purposes of the study if they were performed within the correct time frame and consistent with modified RECIST guidelines for CT or MRI
- CEA, CA19-9
- Concomitant medications
- Adverse events must be captured from time of consent
- Mandatory baseline fresh biopsy
- cfDNA sample (mandatory) & cytokines

Screening numbers and Enrollment numbers will be assigned as follows.

-Screening number: S001,S002,S003...

-Enrollment number: E001, E002, E003....

[Type here]

[Type here]

[Type here]

7.3 Treatment Period

The visit schedule is based on day periods. Patients will attend the clinic on every administration during the 1 cycle, and from the 2cycle attend the clinic every 3 weeks. The following assessments will be performed at time points specified in the study schedule (appendix 1)

- Vital sign measurements, including temperature, pulse rate, respiration rate, and BP, should be obtained before, during, and at the completion of each infusion of ramucirumab and pembrolizumab.
- Physical examination including ECOG performance status
- Hematology and clinical chemistry
- coagulation profiles;
- Urinalysis (every cycle)
- TFT(every cycle)
- AE (every visit)
- Concomitant medications (every visit)
- Tumor assessments via CT or MRI (every 6 weeks until objective disease progression)
- CEA,CA19-9 ,every tumor assessment
- cfDNA(mandatory), every tumor assessment

It is important to follow the assessment schedule as closely as possible. If scans are performed outside of the scheduled visit \pm 1 week window interval and the patient has not progressed, every attempt should be made to perform the subsequent scans at their scheduled time points. Patients will be evaluated until objective disease progression by modified RECIST1.1, as per the study schedule (see Appendix 1), and then followed for survival, regardless of whether study treatment is discontinued or delayed and/or protocol violations, unless they withdraw consent.

7.4 End of Therapy

Patients should be discontinued from study treatment if any discontinuation criteria are fulfilled. The assessments to be carried out at the visit are detailed in the study schedule

- Physical examination including ECOG performance status
- Vital Sign
- hematology, chemistry, and coagulation profiles;
- Urinalysis
- Imaging studies with tumor measurements/disease response assessments if the patient was discontinued for reasons other than PD;
- ~~Fresh Biopsy sample prior to dosing and at documented disease progression (if feasible)~~
- CEA,CA19-9
- cfDNA

- Concomitant medications & AE

7.5 Post-Treatment Follow-Up Evaluations

Follow-up safety evaluations will occur 30 days (\pm 7 days) after last dose of study drug or until resolution of any drug-related toxicity (telephone contact is acceptable). All patients will be followed for a minimum 30 days after discontinuation of the study drug. All AEs or SAEs occurring during the 30-day post treatment safety follow-up period will be captured. Unresolved study drug related AEs and SAEs at the time of treatment discontinuation or new study drug related AEs and SAEs that occur during the 30-day safety follow-up period will be followed until they have, in opinion of the Investigator, resolved to baseline, have stabilized, or are deemed to be irreversible.

7.6 Survival Follow-up

Once a subject experiences confirmed disease progression or starts a new anti-cancer therapy, the subject moves into the survival follow-up phase and should be contacted by telephone every 12 weeks to assess for survival status until death, withdrawal of consent, or the end of the study, whichever occurs first.

7.7 Follow-Up

Follow-up and treatment of patients post discontinuation ramucirumab/pembrolizumab is at the discretion of the treating physician. The attending physician will be asked to complete the final case report form (CRF) indicating whether he/she believed the patient derived benefit from ramucirumab/pembrolizumab and whether there are plans to commence another form of systemic therapy.

8. TREATMENT

8.1 Treatments Administered

8.1.1 Ramucirumab

Different drug product lots must not be mixed in a single infusion.

Patients will receive 8 mg/kg of ramucirumab every 2 weeks, administered as an I.V. infusion over approximately 1 hour (maximum infusion rate 25 mg/min). The dose of ramucirumab will be dependent upon the patient's baseline body weight in kilograms. This dose will be recalculated if there is a $\geq 10\%$ change in body weight from baseline. Refer to the IB for more details.

8.1.2 Pembrolizumab

Pembrolizumab 200 mg will be administered as a 30 minute IV infusion every 3 weeks. Sites
[Type here] [Type here] [Type here]

Pembrolizumab + Ramucirumab (Ver 2.5, Oct 2024)

should make every effort to target infusion timing to be as close to 30 minutes as possible.

However, given the variability of infusion pumps from site to site, a window of -5 minutes and +10 minutes is permitted (i.e., infusion time is 30 minutes: -5 min/+10 min).

8.2 Materials and Supplies

For instructions on reconstitution and administration of ramucirumab, refer to the IB (Safe Handling and Administration). Calculate the dose and volume of ramucirumab needed to prepare the infusion solution. Vials contain either 100 mg or 500 mg as a 10 mg/mL solution of ramucirumab. Only use sterile sodium chloride (0.9%) solution for injection as a diluent.

Administer via an infusion pump. A separate infusion line must be used for the infusion and the line must be flushed with sterile sodium chloride (0.9%) solution for injection at the end of the infusion.

As infusion-related reactions (IRRs) may occur during or after the administration of ramucirumab, premedication is recommended with a histamine H1 antagonist (such as, diphenhydramine hydrochloride or equivalent) intravenously prior to administration of ramucirumab.

If a patient experiences a Grade 1 or 2 IRR, premedication must be given for all subsequent infusions. If a patient has a second Grade 1 or 2 IRR, administer dexamethasone (or equivalent); then, for subsequent infusions, premedicate with diphenhydramine hydrochloride (or equivalent)

Vials should be stored in a refrigerator at 2°C to 8°C (36°F to 46°F) until time of use. Keep the vial in the outer carton in order to protect from light. DO NOT FREEZE OR SHAKE the vial.

The chemical and physical stability for the ramucirumab infusion solution was demonstrated for up to 24 hours at 2°C to 8°C (36°F to 46°F) or for 4 hours at room temperature (below 25°C (77°F)). DO NOT FREEZE OR SHAKE the ramucirumab infusion solution.

8.3 METHOD OF ASSIGNMENT TO TREATMENT

This is a single-arm study and all patients enrolled will receive ramucirumab/pembrolizumab.

8.4 Special Treatment Considerations

8.4.1 Dose Adjustments and Delays

Ramucirumab

Dose modifications are permitted for ramucirumab in the setting of non-life-threatening, reversible Grade 3 and 4 AEs (that is, fatigue, anorexia, or fever) that resolve to Grade ≤ 1 within 1 treatment cycle (approximately 2 weeks). In this setting, ramucirumab may be readministered. If a second
[Type here] [Type here] [Type here]

Pembrolizumab + Ramucirumab (Ver 2.5, Oct 2024)

instance of such an event occurs, ramucirumab should be subsequently readministered at a dose of 6 mg/kg every other week. A second dose reduction to 5 mg/kg every other week is permitted for this level of event (Grade 3 and 4). If a Grade 4 AE occurs and is deemed at least possibly related to ramucirumab, then ramucirumab should be discontinued except in specific case of Grade 4 fever or Grade 4 laboratory abnormalities. If Grade 4 fever or laboratory abnormalities resolve to Grade ≤ 1 or pretreatment baseline within one treatment cycle (approximately 2 weeks), treatment with ramucirumab may be continued at the discretion of the treating physician. Criteria for dose reduction in the setting of hypertension or proteinuria and other AESIs are detailed in Section 11

Patients who enter the study with symptoms or laboratory values equivalent to NCI-CTCAE Version 4.03 Grade 1 to 2 AEs should not have dose reductions related to the persistence or mild worsening of those symptoms or laboratory values; dose reductions may be warranted if worsening of symptoms or laboratory values is clinically significant in the opinion of the patient's physician. Asymptomatic Grade 3 to 4 laboratory abnormalities should not result in dose interruptions, modifications, or discontinuation of protocol therapy unless determined to be clinically significant by the patient's physician (or unless otherwise specified in this protocol).

The treatment schedule remains static regardless of interruptions in ramucirumab administration. Dose delays are only permitted within 3 days after the date of a regularly scheduled treatment. If a patient is unable to receive treatment on or within 3 days before or after the date of his/her regularly scheduled dose for any reason (including AEs), the next dose of ramucirumab should be administered at the first regularly scheduled treatment time point following the resolution of the event causing the delay. (Treatment in this situation [missed dose/cycle] is considered to occur at the subsequently numbered cycle.) Make-up doses occurring between regularly scheduled, every-treatment time points are not recommended.

The patient's physician may discontinue ramucirumab for lack of disease control or toxicity. Patients who experience an AE requiring dose reduction after 2 prior dose reductions should discontinue ramucirumab therapy. In addition, the patient's physician may withdraw a patient from ramucirumab for disease progression, toxicity, or if the treating physician team determines it is in the patient's best interests for any reason. Patients whose performance status worsens by ≥ 2 units should be discontinued from study therapy.

After termination of ramucirumab therapy, the patient will be treated as clinically indicated by the treating physician.

Pembrolizumab

Adverse events (both non-serious and serious) associated with pembrolizumab exposure may represent an immunologic etiology. These adverse events may occur shortly after the first dose or
[Type here] [Type here] [Type here]

Pembrolizumab + Ramucirumab(Ver 2.5, Oct 2024)

several months after the last dose of treatment. Pembrolizumab must be withheld for drug-related toxicities and severe or life-threatening AEs as per Table below. Events of Clinical Interest Guidance Document for supportive care guidelines, including use of corticosteroids.

Dose Modification Guidelines for Drug-Related Adverse Events

Toxicity	Hold Treatment For Grade	Timing for Restarting Treatment	Discontinue Subject
Diarrhea/Colitis	2-3	Toxicity resolves to Grade 0-1.	Toxicity does not resolve within 12 weeks of last dose or inability to reduce corticosteroid to 10 mg or less of prednisone or equivalent per day within 12 weeks.
	4	Permanently discontinue	Permanently discontinue
AST, ALT, or Increased Bilirubin	2	Toxicity resolves to Grade 0-1	Toxicity does not resolve within 12 weeks of last dose.
	3-4	Permanently discontinue (see exception below) ¹	Permanently discontinue
Type 1 diabetes mellitus (if new onset) or Hyperglycemia	T1DM or 3-4	Hold pembrolizumab for new onset Type 1 diabetes mellitus or Grade 3-4 hyperglycemia associated with evidence of beta cell failure.	Resume pembrolizumab when patients are clinically and metabolically stable.
Hypophysitis	2-3	Toxicity resolves to Grade 0-1	Toxicity does not resolve within 12 weeks of last dose or inability to reduce corticosteroid to 10 mg or less of prednisone or equivalent per day within 12 weeks.
	4	Permanently discontinue	Permanently discontinue
Hyperthyroidism	3	Toxicity resolves to Grade 0-1	Toxicity does not resolve within 12 weeks of last dose or inability to reduce corticosteroid to 10 mg or less of prednisone or equivalent per day within 12 weeks.
	4	Permanently discontinue	Permanently discontinue
Hypothyroidism	2-4	Therapy with pembrolizumab can be continued while treatment for the thyroid disorder is instituted	Therapy with pembrolizumab can be continued while treatment for the thyroid disorder is instituted.
Infusion Reaction	3-4	Permanently discontinue	Permanently discontinue
Pneumonitis	2	Toxicity resolves to Grade 0-1	Toxicity does not resolve within 12 weeks of last dose or inability to reduce corticosteroid to 10 mg or less of prednisone or equivalent per day within 12 weeks.
	3-4	Permanently discontinue	Permanently discontinue
Renal Failure or Nephritis	2	Toxicity resolves to Grade 0-1	Toxicity does not resolve within 12 weeks of last dose or inability to reduce corticosteroid to 10 mg or less of prednisone or equivalent per day within 12 weeks.
	3-4	Permanently discontinue	Permanently discontinue
All Other Drug-Related Toxicity ²	3 or Severe	Toxicity resolves to Grade 0-1	Toxicity does not resolve within 12 weeks of last dose or inability to reduce corticosteroid to 10 mg or less of prednisone or equivalent per day within 12 weeks.
	4	Permanently discontinue	Permanently discontinue
Note: Permanently discontinue for any severe or Grade 3 drug-related AE that recurs or any life-threatening event. ¹ For patients with liver metastasis who begin treatment with Grade 2 AST or ALT, if AST or ALT increases by greater than or equal to 50% relative to baseline and lasts for at least 1 week then patients should be discontinued. ² Patients with intolerable or persistent Grade 2 drug-related AE may hold study medication at physician discretion. Permanently discontinue study drug for persistent Grade 2 adverse reactions for which treatment with study drug has been held, that do not recover to Grade 0-1 within 12 weeks of the last dose.			

Dosing interruptions are permitted in the case of medical / surgical events or logistical reasons not related to study therapy (e.g., elective surgery, unrelated medical events, patient vacation, and/or holidays). Subjects should be placed back on study therapy within 3 weeks of the scheduled interruption. The reason for interruption should be documented in the patient's study record.

[Type here]

[Type here]

[Type here]

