	
For patients with only non-measurable disease from at baseline, categorization of objective tumor response assessment will be based on the modified RECIST 1.1 response criteria: CR, PD, non-CR/non-PD.
 
If the investigator is not sure whether progression has occurred, especially if there is a reaction to a non-target lesion (NTL) or a new lesion develops, if clinically necessary, dosing can be continued before next scheduled visit and be advisable to re-evaluate the patient's condition.
 
If progress is confirmed in the repeat scan, the progress date should be declared as the first scan date.
 
Secondary efficacy assessment will be conducted as follows:
 
 Best Overall Response Rate (BORR) is defined as the proportion of the patients who have achieved CR or PR at least once. Disease Control Rate (DCR) is defined as the proportion of the patients with a documented CR, PR, and SD (results will be provided by confirmed and unconfirmed). Progression-Free Survival (PFS) is defined as the time from first administration of investigational drug to the earlier date of PD or death due to any cause. Overall Survival (OS) is defined as the time from first administration of investigational drug to death due to any cause. Duration of Overall Response (DOR) is defined as the time from the first date of assessment as CR or PR to the earlier date of PD or death due to any cause. Maximal Tumor Shrinkage(MTS) is defined as rate of change in tumor size relative to the baseline at the time of best improvement. 
2. Safety assessment
 
The severity of all AEs will be graded for laboratory toxicity and symptoms according to NCI-CTCAE Ver. 5.0. For the events that are not pre-defined in terms under NCI-CTCAE, Investigator should assign a numeric grade of “1” to “5” using the definitions as Mild, Moderate, Severe, Life-threatening, Death, respectively based on maximal intensity.
 
3. Biomarker assessment
 
To collect and store diagnostic and/or archival tumour samples and any fresh tumour biopsies (pre-treatment if clinically feasible and before 3 cycles if clinically feasible) for potential future exploratory research into factors that may influence development and/or response to ramucirumab in combination with pembrolizumab. Next generation sequencing from these samples and/or other protein based exploratory analysis will be carried out. Fresh tissues at baseline is required if clinically feasible

--	---

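### Section 8.4.1 gives two opposite actions for possibly related, reversible Grade 4 fatigue or anorexia on ramucirumab

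*Combined protocol and SAP*

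**What the plan says.** All the relevant text is in the ramucirumab part of Section 8.4.1, Dose Adjustments and Delays.

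The first rule permits re-dosing. It starts "Dose modifications are permitted for ramucirumab in the setting of non-life-threatening, reversible Grade 3 and 4 AEs (that is, fatigue, anorexia, or fever" and requires resolution to Grade 1 or lower "within 1 treatment cycle (approximately 2 weeks). In this setting, ramucirumab may be readministered". For a second such event the instruction is "instance of such an event occurs, ramucirumab should be subsequently readministered at a dose of 6 mg/kg every other week". The rule then adds: "A second dose reduction to 5 mg/kg every other week is permitted for this level of event (Grade 3 and 4". Grade 4 is thus named twice. Nothing in the rule turns on whether the event is attributed to the drug.

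The second rule follows directly: "If a Grade 4 AE occurs and is deemed at least possibly related to ramucirumab, then ramucirumab should be discontinued except in specific case". The exceptions it goes on to list are fever and laboratory abnormalities of Grade 4. If these resolve within about 2 weeks, the treating physician may continue ramucirumab.

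**The concern.** The two rules sit in one paragraph and overlap in scope, but they end differently. One says that ramucirumab may be given again, with reduced doses for repeat events. The other says that it should be discontinued. Fatigue and anorexia are two of the three events named in the first rule, and neither is excepted in the second.

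Two physicians reading the paragraph in good faith could treat the same patient differently. The first stake is patient safety, because this is a stopping rule for a serious toxicity. The second is the record: whether the patient counts as a toxicity discontinuation, and whether re-dosing counts as a protocol deviation, would depend on the reader.

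The uncertainty can also carry over to the other drug. Section 7.1 stops pembrolizumab when ramucirumab stops, while the synopsis continues pembrolizumab if ramucirumab is stopped for intolerable toxicity. That is a separate discrepancy, but it makes an unclear ramucirumab stop more consequential.

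**Working it through.** No arithmetic applies, because the point concerns the consistency of two rules. The check takes each type of event in turn and asks what each rule does with it. In the table, the conditions are those of the first rule: not life-threatening, reversible, and down to Grade 1 or lower in about 2 weeks.

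| Event | Re-dosing rule | Discontinuation rule | Result |
|---|---|---|---|
| Grade 3 fatigue, anorexia or fever, conditions met | Applies | Not reached (Grade 4 only) | Consistent |
| Grade 4 fever, conditions met | Applies | Excepted | Consistent |
| Grade 4 laboratory abnormality | Not listed | Excepted | Consistent |
| Grade 4 fatigue or anorexia, judged unrelated, conditions met | Applies | Does not apply | Consistent |
| Grade 4 fatigue or anorexia, possibly related, conditions not met | Does not apply | Discontinue | Consistent |
| Grade 4 fatigue or anorexia, possibly related, conditions met | May be given again | Discontinue | **Conflict** |

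Only the last row conflicts.

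The next step is to look for text elsewhere that settles that row.

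- The rest of Section 8.4.1 stops ramucirumab when a further reduction would be needed after two, and when performance status worsens by 2 or more units. Section 14.3 repeats the performance-status rule. These are separate triggers and do not rank the two sentences.
- Section 6.3 leaves unacceptable toxicity to the judgement of the participant or investigator.
- Section 11.1 deals with named events of special interest. Fatigue and anorexia are not among them.
- Appendix 2 has no general rule for Grade 4 events.

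The last step is to ask how much Grade 4 fatigue or anorexia would be left to the first rule if the second were taken to prevail: only events judged unrelated. Under Section 10.2.2 that group is likely to be small. An event counts as possibly related when a causal link is improbable but cannot be ruled out, and an event whose cause the physician cannot determine is also classed as related. For fatigue and anorexia, the dose reductions that the first rule sets out for Grade 4 would then serve mainly events not attributed to the drug.

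**The case against.** The strongest reply is that the paragraph can be read in sequence. The first rule is general and permissive. The later one is directive and narrower, since it covers Grade 4 only and requires possible relatedness. Read as a rule followed by a carve-out, the first still governs qualifying Grade 3 events, Grade 4 fever, and unrelated Grade 4 fatigue or anorexia. This reading is plausible, and because of it one should not say that the two actions are equally well supported by the text. But the carve-out is not written. The sentences have no cross-reference or order of precedence, and the first rule names fatigue, anorexia and Grade 4 expressly.

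Three stronger readings are tempting, and the documents support none of them.

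- A reader might infer that every possibly related Grade 4 fatigue or anorexia event is caught. It is not. An event that fails any of the first rule's conditions meets only the discontinuation sentence.
- A reader might infer that a Grade 4 event that is not life-threatening is a contradiction in terms, because the synopsis grades events "using the definitions as Mild, Moderate, Severe, Life-threatening, Death, respectively based on maximal intensity". That scale is a fallback for events without a CTCAE term, and the documents do not show that fatigue, anorexia or fever fall under it. Section 8.4.1 itself refers to asymptomatic Grade 4 laboratory findings. It follows that deleting the qualifier is not a neutral tidy-up: it limits which events allow re-dosing, so removing it would change a clinical rule.
- A reader might infer damage to the efficacy analysis. Section 13.1.1 counts every patient with at least one dose in the response-rate denominator, and Section 13.2 plans descriptive safety summaries without tests.

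**Conclusion.** The conflict is real but narrow. It concerns Grade 4 fatigue or anorexia that is at least possibly related to ramucirumab, is not life-threatening, is reversible, and resolves to Grade 1 or lower in about 2 weeks. For that event the protocol states two opposite actions and gives no order of precedence.

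Its frequency cannot be sized. The documents give no expected rate of such events and no CTCAE grade definitions for fatigue or anorexia, and the performance-status and investigator-judgement stops may remove some of these patients anyway. The Simon design in Section 12, with its threshold of at least 7 responses in 25 evaluable patients, does not depend on it. The point should be corrected because it concerns a safety instruction and the correction is cheap. It does not threaten the primary result.

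The conclusion rests on reading the paragraph as written, without supplying an override that it does not state.

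**What to change.** The sponsor should reconcile the two sentences in Section 8.4.1 so that a possibly related, reversible Grade 4 fatigue or anorexia event has one stated action, and should say explicitly how the discontinuation sentence relates to the re-dosing rule before it. Which action applies is a clinical decision for the sponsor, and this review takes no position on it. The limitation to events that are not life-threatening need not be touched for this purpose.

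The cost is a wording amendment to one section. The sample size and the analysis plan do not change.

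### Two rows of the pembrolizumab dose-modification table (T1DM/hyperglycemia and hypothyroidism) conflict with the permanent-discontinuation Note printed under the same table

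*Combined protocol and SAP*

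**What the plan says.** Section 8.4.1 gives a table of pembrolizumab dose modifications for drug-related adverse events. Its columns are the toxicity, the grades for which treatment is held, the timing of restart, and the rule for discontinuing the subject. The Note beneath it states: "Permanently discontinue for any severe or Grade 3 drug-related AE that recurs or any life-threatening event".

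The type 1 diabetes/hyperglycemia row covers T1DM or Grades 3-4. Its restart cell says "Hold pembrolizumab for new onset Type 1 diabetes mellitus or Grade 3-4 hyperglycemia associated with evidence of beta cell failure", and its Discontinue Subject cell says "Resume pembrolizumab when patients are clinically and metabolically stable".

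The hypothyroidism row lists Grades 2-4 in the hold column. Its restart and discontinuation cells carry the same sentence: "Therapy with pembrolizumab can be continued while treatment for the thyroid disorder is instituted".

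One row, AST/ALT/bilirubin at Grade 3-4, points to a footnoted exception. That footnote is limited in scope: "For patients with liver metastasis who begin treatment with Grade 2 AST or ALT".

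**The concern.** The Note and the two rows cover overlapping events and direct opposite actions. A physician whose patient has a life-threatening endocrine event on pembrolizumab can find, in one table, an instruction to stop for good and an instruction to resume or a permission to continue. Either course follows one part of the protocol and breaches another.

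What is at stake is patient safety and equal handling of like cases. The same event could end treatment for one patient and lead to re-exposure for another, depending on which line the physician reads. This is a single-center trial, so the inconsistency would arise between treating physicians rather than between sites.

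Section 11.2 names diabetic ketoacidosis within the type 1 diabetes category, so a serious event of this kind is one that the protocol itself foresees.

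**Working it through.** There is no arithmetic to reproduce beyond a count of rows. The check sets each row against the Note and then looks for text elsewhere that would resolve a difference.

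**Step 1. Each row at Grade 4.** The table has 10 toxicity categories.

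| Category | Instruction at Grade 4 | Agrees with the Note? |
|---|---|---|
| Diarrhea/colitis | Stop permanently | Yes |
| AST, ALT or bilirubin | Stop permanently, with a flagged exception (footnote 1) | Yes, subject to that exception |
| T1DM/hyperglycemia | Hold, then resume when stable | No |
| Hypophysitis | Stop permanently | Yes |
| Hyperthyroidism | Stop permanently | Yes |
| Hypothyroidism | May continue | No |
| Infusion reaction | Stop permanently | Yes |
| Pneumonitis | Stop permanently | Yes |
| Renal failure/nephritis | Stop permanently | Yes |
| All other drug-related toxicity | Stop permanently | Yes |

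Eight of 10 agree, one of them with a footnoted carve-out; 10 - 8 = 2 do not.

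**Step 2. Recurrent Grade 3.** The Note also requires a permanent stop when a severe or Grade 3 drug-related event recurs. The hyperglycemia row treats Grades 3 and 4 together and sets no limit on how often the drug may be resumed. A second Grade 3 hyperglycemia that meets the row's beta-cell condition therefore also gets two answers. For hypothyroidism the recurrence conflict is not clearly shown: the row describes a disorder under continuing treatment and has no resolution step from which an event could recur.

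**Step 3. The rows against their own column headings.** The hyperglycemia row has an instruction to resume where a discontinuation rule belongs, and so states no discontinuation rule. The hypothyroidism row lists grades to hold for, yet neither of its other cells describes a hold.

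**Step 4. From Grade 4 to life-threatening.** The Note speaks of life-threatening events, not of Grade 4. The synopsis (Safety assessment) assigns grades 1 to 5 "using the definitions as Mild, Moderate, Severe, Life-threatening, Death, respectively based on maximal intensity", but formally only for events that the CTCAE does not pre-define. Section 10.2.6 (infusion reactions to each drug) and Section 11.1.1 (hypertension) also describe Grade 4 as life-threatening. The link is a reasonable inference from this wording; no text states it for hyperglycemia or hypothyroidism. The recurrent Grade 3 conflict does not depend on it.

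**Step 5. Other text that might resolve the conflict.**
- Section 6.3 allows discontinuation for unacceptable toxicity or in the patient's best interests, and for a Day 1 delay of more than 28 days due to treatment-related events. It does not say whether the row or the Note governs.
- Section 11.2 gives insulin and work-up for hyperglycemia and hormone replacement for hypothyroidism. It has no discontinuation rule for either.
- The sentence in Section 8.4.1 on asymptomatic Grade 3 to 4 laboratory abnormalities stands under ramucirumab, covers asymptomatic findings only, and gives way to anything the protocol specifies elsewhere.

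Nothing states that a row overrides the Note, or the reverse.

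**The case against.** The strongest reply is that the specific governs the general. The two rows name the event and its grades, the Note is a general statement, the table is presented as guidelines, and the hypothyroidism wording is permissive rather than mandatory. A physician might well read the rows as deliberate endocrine exceptions.

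That reading is possible, but the protocol does not state it, and two features of the table weigh against assuming it. The drafters marked an exception where they wanted one, in the AST/ALT/bilirubin row, and marked none in these two. And because the other categories already stop at Grade 4, the Note's life-threatening clause adds little for graded drug-related toxicity if it does not reach these rows. What stands is that the permissive hypothyroidism wording makes the clash there softer than a direct order against an order.

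A reader might also infer three stronger things that the documents do not support.
- That this table is the only rule on stopping pembrolizumab. Section 6.3, the infusion-reaction table in Section 10.2.6 and the performance-status rule in Section 14.3 also apply.
- That Sections 8.4.1 and 11.2 contradict each other on the hyperglycemia trigger. Beta cell failure governs a drug hold, while ketosis or metabolic acidosis governs insulin and work-up. These are different actions.
- That discontinuation for toxicity, or PFS and duration of response, becomes uninterpretable. Sections 7.3 and 10.1.1 continue tumor assessment to objective progression after treatment stops, Section 7.3 adds survival follow-up, Section 6.3 requires reasons for stopping to be recorded, and Section 13.2 makes safety descriptive.

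**Conclusion.** The contradiction holds, within limits. Two of the 10 categories conflict with the Note for a life-threatening (Grade 4) event, and the hyperglycemia row conflicts with it for a recurrent Grade 3 event as well. Both rows also disagree with their own column headings.

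The Grade 4 part rests on reading Grade 4 as life-threatening. The hyperglycemia part applies only to new-onset T1DM or to Grade 3-4 hyperglycemia with evidence of beta cell failure. With no event rates in the documents, the expected number of affected patients is unknown.

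The consequence is for patient safety and consistent treatment. ORR under Section 13.1.1 counts all patients who received at least one dose, and the two-stage design in Section 12 does not depend on these rows. Neither is affected, nor is follow-up for PFS and OS.

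**What to change.** The sponsor should reconcile the Note with the T1DM/hyperglycemia and hypothyroidism rows so that each event and grade has one instruction, including recurrence of Grade 3 hyperglycemia. This can be done by naming the exceptions, with grades, in the Note, or by changing the rows to agree with it. That choice is the sponsor's clinical decision, and none is recommended here.

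In the same edit, the Discontinue Subject cell of the hyperglycemia row should match its heading, by stating a discontinuation rule or stating that there is none. The grades listed under the hold heading for hypothyroidism should be made consistent with the rest of that row. If the Note is meant to apply to Grade 4 as such, it should say so.

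The cost is a wording amendment to one table and its Note. It adds no procedures and changes neither the sample size nor the analysis.
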